Study Title: A pilot cluster randomized controlled trial of a phone intervention supporting family caregivers of people living with dementia in Vietnam: Resources for Enhancing Alzheimer's Caregiver Health in Vietnam (REACH VN)

NCT#: NCT05481320

Document Date: November 16, 2022

Document Type: Study Protocol

1) Protocol Title

Title: A Phone Intervention for Family Dementia Caregivers in Vietnam

Protocol Version Date: *11/16/2022*

2) Objectives

The objective of this study is to examine the feasibility, acceptability, and preliminary efficacy of the phone version of REACH VN, a psychosocial culturally adapted Alzheimer's family caregiving intervention that will be delivered over the phone with an enhanced control as the comparison. The pilot cluster RCT will test the hypothesis that family caregivers who receive the intervention will show lower caregiver burden (primary outcome) and lower depressive/anxiety symptoms (secondary outcome) compared with those in the control group.

3) Background

Low- and middle-income countries (LMIC) such as Vietnam are undergoing a dramatic demographic transition that will result in a substantial increase in the number of older adults, including those afflicted with Alzheimer's disease and related dementias (ADRD), over the next several decades. Dementia is among the most disabling and costly neurodegenerative brain diseases. Strengthening LMIC capacity to support family caregivers of people with dementia through low-cost and sustainable non-pharmacological approaches, such as education and skill-building to deal with difficult behaviors, is vital to avoid costly and ineffective alternatives such as psychotropic medications or institutionalization, and to reduce caregiver burdens and depression. While evidence-based non-pharmacological treatments exist in high income countries (HIC), these interventions have not been adapted for use in Vietnam and other LMIC.

Delivery of interventions through telehealth and other types of technology (e.g., online, mobile apps) holds considerable promise for the field because of lower costs and greater reach, particularly for those living in rural areas. These considerations are particularly important in Vietnam and other LMIC because most older adults reside in rural areas. With the rapid adoption of mobile phones, tablets, and smartphones, family caregiver interventions hold considerable promise for closing gaps in dementia care and services for these countries. The COVID-19 pandemic has also reinforced the need for interventions that can be delivered at a distance to maintain support for caregivers and reduce their social isolation.

To our knowledge, our study will be the first study in Vietnam or other LMIC in Asia to examine the efficacy of multicomponent family caregiver intervention delivered remotely. The intervention has several components (e.g.,

PROTOCOL TITLE: A Phone Intervention for Family Dementia Caregivers in Vietnam

psychoeducation, stress reduction, skill-building) and is designed to reduce caregiver stress and burden.

4) Inclusion and Exclusion Criteria

Inclusion criteria:

To be eligible to participate, a family member will need to be the identified adult (i.e., age 18 and above) who is the primary informal (i.e., unpaid family member) caregiver (i.e., the person who provides the most time day-to-day care) to an older adult (i.e., age 60 and above) with dementia living in the community. If the primary caregiver is not available to participate, an alternate family member who provides substantial care (i.e., at least 4 h/day) to an older adult with dementia will be eligible to participate. In addition, caregivers will need to score ≥ 6 on the Zarit Burden Interview-4 (ZBI-4). All participants will be living in clusters in Thach That District, a semi-rural area in Hanoi.

Exclusion criteria:

The study will exclude:

- Caregivers with difficulties in the consent process due to cognitive impairment or severe sensory impairment (i.e., visual, hearing)
- Caregivers don't have access to phone
- Individuals who are not yet adults (i.e., infants, children, teenagers)
- Prisoners

5) Study Timelines

- We plan to begin recruitment in August of 2022.
- We plan to complete recruitment by January of 2023.
- We plan to complete all data collection and intervention activities by April of 2023.
- We plan to complete preliminary analyses of the data by July of 2023.

6) Study Endpoints

This is a time-limited intervention lasting up to 3 months with independent assessment of outcomes at baseline and 3 months.

7) Procedures Involved

Study design: A two arm, 3-month follow up, cluster randomized controlled trial of 60 caregivers (30 in REACH VN phone intervention group and 30 in enhanced control group) will be conducted.

Setting: Thach That District, a semi-rural area in Hanoi, Vietnam.

Recruitment:

PROTOCOL TITLE: A Phone Intervention for Family Dementia Caregivers in Vietnam

In collaboration with commune health stations, community-based screening will be conducted to identify “at risk” older adults with dementia and their family caregivers.

Staff from the National Geriatric Hospital (NGH) will train local staff (e.g., village health workers) to identify people at high risk for dementia from their caseloads, including those with a history of significant memory problems, behavioral issues and evidence of functional decline. Staff from local health clinics will contact potential participants by phone or in-person, provide information about the project, and invite them to participate in screening to determine their eligibility. Verbal consent will be obtained from an older adult and a family member prior to screening by research staff. Those who consent to participate in the screening will undergo an assessment including a brief neurological exam, cognitive testing and dementia stage using standardized instruments, including the Mini-Cog, NPI-Q, and CDR. The assessments will be conducted by physicians, neurologists, or healthcare professionals trained by NGH. Once an older adult has been determined to meet criteria for dementia (i.e., CDR ≥ 1), we will identify the adult family member who is providing the most day-to-day care and invite them to participate in a brief screening to determine their eligibility. If they are eligible, we will invite them to participate in the study and obtain verbal consent.

A screening log will be kept to document number and reasons of participants who do not meet the inclusion criteria, decline to participate, or any other reasons.

Consent:

Because of the minimal risk of both screening and behavioral intervention, verbal consent will be obtained for both. As part of the consent process, all caregivers will be informed that this is a voluntary study and that they can withdraw at any time.

Randomization:

Communes will be the unit of randomization and randomization assignments will be generated using a block randomization function in R for each stratum with a 1:1 ratio for two groups: intervention (n= approximately 8 clusters or 30 caregivers) or enhanced usual care (n= approximately 8 clusters or 30 caregivers). The UC Davis Biostatistician will be responsible for generating randomization codes and assigning randomization codes to communes. The biostatistician will communicate cluster assignment to the principal investigator (PI) to convey to the study team in Vietnam of when communes have been randomized.

Clusters will need to be in Thach That District and have a minimum of 3 participants and a maximum of 15 participants.

Blinding:

A trained outcome assessor who conducts data collection will be blinded regarding group assignments.

REACH VN Phone Intervention:

PROTOCOL TITLE: A Phone Intervention for Family Dementia Caregivers in Vietnam

Family caregivers in the intervention will receive a manualized multicomponent intervention, including psychoeducation, stress reduction, and skill-building, that will consist of 4-6 “core” sessions with the option for 1-2 “maintenance” sessions based on caregiver needs and clinical judgment with a trained staff (e.g., nurse, social worker, or community health worker) who has been certified to deliver the intervention. Interventionists will follow the interventionist manual that includes scripts, detailed descriptions of the goals for each session, and standardized forms.

The enrollment session (session 0) will be conducted face-to-face. Interventionists with village health workers will come to caregivers’ home to provide a caregiver notebook with information about dementia and management of common problems, check phone issues and signals, and conduct the risk priority intake assessment. The intervention sessions will be conducted over the phone with either audio or video call over the course of 1-3 months. The sessions will occur every 1–2 weeks depending on the needs and availability of family caregivers. Each intervention session will last between 30 minutes to an hour. In case caregivers are not able to concentrate on the session after the first 20-30 minutes, interventionists can end the session and make appointment to call back within 2-4 days (or whenever it is possible) to complete the session.

At the beginning of the intervention, we will emphasize to caregivers that text message is only allowed for scheduling or making changes to scheduled intervention times, not for other purposes. In case caregivers would like other family members to attend the intervention with them, interventionists will inform caregivers in advance that the intervention includes components that ask caregivers about caregiving difficulties, private psychological issues, or family problems; thus, it is up to caregivers to decide whether to include family members into the calls. If they feel comfortable sharing when there are with other family members, they may choose so to let other family members attend the intervention. However, if caregivers are not comfortable, we will advise them to attend the intervention by themselves.

Quality control of the intervention

At the end of each session, interventionists will complete a standardized treatment form (i.e., Interventionist Delivery Assessment (IA)) that summarizes the session either on REDCap or hardcopy.

For training purposes only and quality control of the intervention, we will audio record a subsample of the intervention sessions. These audio recordings will be stored securely and will not be linked to participant’s name or other identifying information. These will not be used for research purposes. The recordings will be reviewed within 3 months and then destroyed. Participants may continue their

PROTOCOL TITLE: A Phone Intervention for Family Dementia Caregivers in Vietnam

participation in this study without consenting to these recordings and having any impact on their participation.

In general, a session will be conducted by one interventionist. However, in some cases, there will be another interventionist who will join the session as a supportive person to enhance the quality control of the intervention.

Supervision of all interventionists will take place during a weekly supervision meeting (in-person or by phone) with senior members of the research team.

Enhanced Control:

Caregivers in the enhanced control group will receive a single phone session in which they will receive education about ADRD including written materials.

Outcome assessments:

A research assistant at the National Geriatric Hospital who is trained and certified will conduct outcome assessments over the phone. An outcome assessor will be masked to group assignment status. We will remind caregivers not to tell an outcome assessor their group assignment status to minimize bias. Caregivers in both groups will be assessed at baseline and 3 months. The primary outcome will be caregiver burden as assessed by the Zarit 6-item burden scale (ZBI-6) and the secondary outcome will be depressive/anxiety symptoms as assessed by the four-item Patient Health Questionnaire (PHQ-4). We will use previously developed Vietnamese versions of study instruments.

Feasibility, fidelity, and acceptability assessments:

Feasibility metrics will include recruitment, randomization, retention, treatment adherence, treatment fidelity, and assessment processes. *Fidelity assessment* will be based on review of standardized treatment delivery forms completed by interventionists and an independent observer of a random subset of sessions. Prior to the RCT, interventionists who are already certified in face-to-face REACH VN intervention will need to be trained in phone delivery. *Acceptability* will be assessed through semi-structured interviews with a random subset of participants who have completed the intervention group (n=10) and REACH VN interventionists (n=5). These interviews will include questions on satisfaction, aspects of the intervention that participants found most helpful, challenges, and opportunities for improvement. We will inquire about any issues related to intervention delivery by audio or video call.

Reimbursement:

Participants will receive \$4 (or 100,000 VND) at the end of the screening session and \$8 (or 200,000 VND) at the end of each study visit/session (including intervention sessions and outcome assessments).

8) Data and/or Specimen Management and Confidentiality

REDCap will be used to collect outcomes data. Procedures for maintenance and confidentiality include 1) assigning each participant a unique identifier, 2) data collected will be labeled using the unique identifier and will be stored separately

PROTOCOL TITLE: A Phone Intervention for Family Dementia Caregivers in Vietnam

from the key linking personal information (e.g., name, date of birth, address, phone number) and identifiers, 3) data will be kept on a secure server that is only accessible to research staff, 4) at the conclusion of the study, the key linking identifiers and personal information will be destroyed, 5) all research personnel in the U.S. who have access to the patient data will receive training on conducting human research (e.g., NIH online course) – all investigators and research staff in Vietnam will participate in the local equivalent of this training.

9) Data and/or Specimen Banking

All data will be stored on a secure server at in Vietnam. De-identified data will be transferred to UC Davis and the University of Minnesota (UMN) electronically through an encrypted zip file. After the study, the key linking personal identifiers to the survey data will be destroyed.

10) Provisions to Monitor the Data to Ensure the Safety of Subjects

Case review will occur on a weekly basis with a team that includes the interventionists, the PI and investigators from the NGH, UCD, and UMN. The caregiver's level of distress and any indicators of elder abuse/neglect will be reviewed at each session.

This study will have a Safety Officer (SO), who will meet 1-2 times each year to review the progress of the study, including adverse events, procedures for maintaining the confidentiality of data, and the quality of data collection, management, and analyses. The SO will also review any issues that arise in terms of conflict of interest or serious adverse events as needed. The SO will report directly to the funder (i.e., NIA).

[name] will be responsible for overall monitoring and appropriate reporting of adverse events including serious adverse events that occur during the study. Plans regarding reporting of adverse events will follow guidelines and policies of UC Davis as well as NIH.

Adverse events will include events untoward or unfavorable mental or physical health-related occurrence in a human subject that is temporally associated with the subject's participation in the research, regardless of whether they are considered related to the subject's participation in the research. Examples of such events that might occur include incidents of brief hospitalization, caregiver distress or depression, instances of elder abuse or neglect, and other unanticipated events. Serious adverse events will be further defined as those events that seriously jeopardize the participant's health, including prolonged hospitalization, suicide attempts, and death. The overall goal of this plan is to have both serious adverse events (SAE) and non-serious adverse events (NSAE) that are viewed as likely (i.e., 50% or higher) related to study participation reported to both the UCD IRB and NIH in a timely fashion.

As a routine part of training, intervention study staff will be educated to monitor for these events and to report them to the research staff. Interventionists or other research staff will complete AE Field Report Form and provide this to NGH RCT leads (i.e., [name] and [name]) within 48 hours. Upon receiving the report, [name] must confirm that she has received the report and is available to act upon it. [name] will review AE Field Report Form, complete AE Form and, if it is a SAE, complete SAE Form and send to study PIs ([name], [name], and [name]) within 48 hours. [name] will serve as back-up in case [name] is not available. Within 2 working days of receipt of the information about the SAE, [name] will share this information with the research team and the SO. If the SAE is viewed as likely (i.e., >50% probability) of being related to participation in the study, the SAE will be reported to the UCD IRB and to NIH within 2 working days of this determination with the goal of reporting all such events to UCD IRB and to the NIH PO within 5 working days of the time [name] became aware of the event. NSAE will be shared with the core members of the research team, including Drs. [name], [name] and [name], at their regular biweekly meetings. If NSAE are deemed as possibly related to study participation they will be reported to the SO within one week and, if the SO views them as “probably” (i.e., >50% likelihood) of being related to study participation, to the UCD IRB and NIH PO within 5 working days. All SAE and NSAE that are viewed as not likely to be related to research participation will be reported on an annual basis to the NIH PO as part of the progress report as well as to the IRBs.

11) Withdrawal of Subjects

Subjects (patients and family members) may withdraw at any time. If they withdraw from the study, they will be given the option of having their records destroyed.

12) Risks to Subjects

The main risks associated with this study: 1) discomfort or mild distress because of the intervention, 2) inconvenience because of the need to fill out the study questionnaires, and 3) loss of confidentiality. These risks are similar to the risk of undergoing routine assessments in healthcare clinics in Vietnam. Specific steps are being taken to address each category of risk (please see Section 16).

13) Potential Benefits to Subjects

There are several potential direct benefits to subjects. Caregivers may experience an increase in their knowledge and skills because of the intervention. In addition, caregivers will learn stress reduction techniques that may help reduce caregiving-related distress. Older adults participating in screening will be given the option of

having information about their cognitive testing be provided to their primary care physician.

14) Multi-Site Research

This is a single-site, multiple PIs, international study with [name] as the lead investigator. Approval for the study will be obtained by both the UC Davis IRB and the Vietnam National Geriatric Hospital IRB. [name] will be responsible for coordinating with the international site to ensure that the most current version of the protocol and consent document are used. He will work with the PI at the Vietnam National Geriatric Hospital to ensure that 1) Participating sites will safeguard data as required by local information security policies, 2) All local site investigators conduct the study appropriately, and 3) All non-compliance with the study protocol or applicable requirements will be reported in accordance with local policy.

15) Community-Based Participatory Research

NA

16) Provisions to Protect the Privacy Interests of Subjects

Discomfort due to the intervention: Even though this study builds on evidence-based strategies for support of family caregivers, subjects may experience discomfort or mild distress when discussing their caregiving experience or because of concerns about confidentiality. These risks will be minimized in several ways. Interventionists will be trained to enhance their skills to be empathetic listeners to create an emotionally comfortable environment for family caregivers. Interventionists will be trained to remind patients that they are not required to answer any questions and can withdraw from the intervention at any time or choose to end a session early. For extreme situations of emotional stress (e.g., involving threats of self-harm), interventionists will have an established protocol in emergency situations to minimize risk of harm.

Inconvenience due to questionnaires: Some of the survey questions might make participants feel uncomfortable or upset. During the consent process, participants will be advised that they can choose not to answer any questions that make them feel uncomfortable. Risks to subjects are minimal for several reasons.

Loss of confidentiality: Steps will also be taken to protect against risk regarding loss of confidentiality which is particularly important in Vietnam where staff may not be as familiar with research and the importance of confidentiality. All staff will receive training and education about the importance of maintaining confidentiality as a core aspect of the research to minimize risk. When conducting interviews, staff will try to maintain a private space and discuss the participant's level of comfort in talking to the interviewer or interventionist if others are within earshot. In the consent process, participants will be informed

PROTOCOL TITLE: A Phone Intervention for Family Dementia Caregivers in Vietnam

about loss of confidentiality as a risk and the precautions being taken to minimize this.

Other: This is a behavioral intervention and does not involve drug treatment. In prior studies conducted with multi-cultural populations in the United States, there have not been any serious adverse side events attributable to the intervention (personal communication with one of the PIs of a large-scale national study). Similarly, in a pilot study there were no serious adverse events related to this intervention. It is also possible that elder/abuse or neglect may be detected during the study and require intervention. A protocol for handling cases of abuse/neglect according to local norms/resources has been developed in collaboration with our colleagues in Vietnam.

17) Compensation for Research-Related Injury

NA – minimal risk study

18) Economic Burden to Subjects

There are no costs that subjects may be responsible for because of participation in the research.

19) Drugs or Devices

NA

20) [ClinicalTrials.gov](#) Registration

Section 1: NIH Funded Studies

If yes to BOTH, the study must be registered on Clinicaltrials.gov.

Yes	
	This study is funded by the NIH . (If this study is not funded by NIH, go to Section 2.)
	One or more human subjects will be prospectively assigned to one or more interventions (which may include placebo or other control) to evaluate the effects of those interventions on health-related biomedical or behavioral outcomes.

Section 2: Studies subject to FDA jurisdiction

If yes to ANY the study must be registered on Clinicaltrials.gov.

Yes	
	This is a prospective clinical study of health outcomes in human subjects that compares an intervention with an FDA-regulated device against a control. This is not a small clinical trial to determine the feasibility of a device, or a clinical trial to test prototype devices where the primary outcome measure relates to feasibility and not to health outcomes.
	This is a pediatric postmarket surveillance of a device as required under section 522 of the Federal Food, Drug, and Cosmetic Act.

PROTOCOL TITLE: A Phone Intervention for Family Dementia Caregivers in Vietnam

	This is a controlled clinical investigation, other than a phase I clinical investigation, of a drug subject to section 505 of the Federal Food, Drug, and Cosmetic Act or to section 351 of the Public Health Service Act.
--------------------------	--

To view a flowchart describing applicable clinical trials subject to FDA jurisdiction click [here](#).

Section 3: Publishing the results

If yes to BOTH the study must be registered on Clinicaltrials.gov.

Yes	
	This study prospectively assigns people or a group of people to an intervention, with or without concurrent comparison or control groups, to study the cause-and-effect relationship between a health-related intervention and a health outcome.
	The PI has access to and control over all the data from the clinical trial and has the right to publish the results of the trial and plans to publish the results in a journal that follows the ICMJE recommendations .

This requirement includes studies of behavioral interventions.

Section 4: Registration on Clinicaltrials.gov is not required

Yes	
	I have read sections 1-3 above and registration on clinicaltrials.gov is not required for this research.

21) Criteria for 10 Year Approval

If yes to all items below this research may qualify for a 10-year approval period.

Yes	
	This research involves no more than minimal risk.
	This research does not receive any federal or state government funding or funding from a private funder who requires annual review per contract.
	This research is not subject to FDA jurisdiction.
	This research does not include prisoners as participants.
	This research is not subject to SCRO oversight.
	This research is not subject to oversight by the Research Advisory Panel of California (RAP of C).
	This research does not involve identifiable information held by the State of California Department or Agency
	No personnel involved in the design, conduct, or reporting of this research have a new unreported related financial interest (RFI) in this study.

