### *Statistical Analysis Plan*

RCT outcomes include caregiver burden (primary) and depressive/anxiety symptoms (secondary). Preliminary analyses will compare the two groups at baseline on participant characteristics and primary outcomes using t-tests or chi-squared tests as appropriate; non-parametric versions will be used if needed. For each outcome, the primary assessment of efficacy will be based on intent-to-treat analyses. Difference scores on the outcomes between the two assessments will be computed. Within-group change will be assessed with a paired t-test or the Wilcoxon signed rank test, as appropriate, while between-group differences in change will be assessed with a two-sample t-test or the Wilcoxon rank sum test. If groups differ at baseline, analysis of covariance will be used with the 3-month assessment as the outcome and the baseline assessment as a covariate; group will be the primary predictor of interest and any additional participant characteristics found to be different at baseline will also be considered as covariates. Transformations or generalized linear models for non-normal data will be considered if model assumptions are violated. The data were imported into the REDcap database and analyzed using SAS statistical software. A p-value less than 0.05 is considered statistically significant.

Power analysis: With 30 participants per group, we will have 80% power to detect a difference as small as 0.64 standard deviations between the groups, assuming a one-sided test (as this is a pilot study) and alpha=0.05. If alpha is reduced to 0.025 to account for the two outcomes, the minimum detectable difference is 0.72 standard deviations. Our pilot RCT using the original REACH VN showed effect sizes of at least 0.9, so the current study is powered to detect smaller effects, which might be expected in a telehealth administration of the intervention.

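### Communes are randomised within strata, but no planned analysis includes the strata; they should enter a primary analysis that also accounts for commune

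*Protocol*

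**What the plan says.** Protocol section 7, under Randomization, sets the unit ("Communes will be the unit of randomization") and the method, a "block randomization function in R for each stratum", at 1:1. It expects about 8 communes and 30 caregivers per arm, and each commune must "have a minimum of 3 participants and a maximum of 15 participants". This is the only mention of strata. The stratification factor, the number of strata and the block size are not given in the text I have. I have not seen the material that precedes the SAP's analysis text; if the factor is named there, that part of the point falls away.

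In the SAP, "between-group differences in change will be assessed with a two-sample t-test or the Wilcoxon rank sum test". The alternative is conditional: "If groups differ at baseline, analysis of covariance will be used with the 3-month assessment as the outcome and the baseline assessment as a covariate". Beyond the baseline score, "any additional participant characteristics found to be different at baseline will also be considered as covariates". Neither stratum nor commune appears in any planned test or model, or in the power analysis.

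**The concern.** Blocking within strata takes between-stratum variation out of the true error of the arm difference. An analysis that omits the strata still counts that variation in its standard error, so it does not match the way the communes were allocated.

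The SAP's covariate rule does not repair this, for two reasons. It is written for participant characteristics, whereas a factor used to stratify communes is normally a property of the commune. It also selects on observed imbalance, and blocking is meant to prevent imbalance in this factor. The rule therefore tends to exclude the one factor that the design fixed in advance.

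At stake is precision in a trial with about 16 randomised units, if the strata carry information about the outcome. There is a second risk: that the omission is mended in a way that makes the test worse, because the same test also ignores commune.

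**Working it through.** **1. The SAP's own figures.** Inputs from the SAP: 30 per group, 80% power, one-sided alpha 0.05 or 0.025. Detectable difference = (z for 1−alpha + z for 0.80) × √(2/30).

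- alpha 0.05: (1.645 + 0.842) × 0.2582 = 0.642 SD (stated 0.64).
- alpha 0.025: (1.960 + 0.842) × 0.2582 = 0.723 SD (stated 0.72).

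The figures reproduce. They assume independent caregivers, with no strata and no clustering.

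**2. Assumed quantities.** The documents give neither the share of outcome variance explained by stratum (R²) nor the residual correlation within communes (ICC). I use R² of 0, 0.10 and 0.20 and ICC of 0, 0.05 and 0.10.

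**3. Simulation.** There are 16 communes of 3 or 4 caregivers (60 in all, mean 60/16 = 3.75) in two equal strata. Half the communes in each stratum go to each arm. The outcome is normal with non-treatment variance 1, the test is one-sided at 0.05, and the effect for power is 0.64 SD. Each cell has 8,000 runs, so the Monte Carlo standard error of a 5% rate is √(0.05 × 0.95/8000) = 0.0024. Entries are without / with a stratum term.

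| Analysis | R² | ICC | Type I error | Power (%) |
|---|---|---|---|---|
| Individual-level | 0 | 0 | 0.050 / 0.049 | 78.8 / 78.6 |
| Individual-level | 0.10 | 0 | 0.039 / 0.046 | 80.0 / 82.8 |
| Individual-level | 0.20 | 0 | 0.037 / 0.054 | 80.9 / 85.9 |
| Individual-level | 0.10 | 0.05 | 0.054 / 0.064 | 79.5 / 82.1 |
| Individual-level | 0.10 | 0.10 | 0.062 / 0.073 | 78.4 / 80.7 |
| Commune means | 0 | 0.05 | 0.048 / 0.047 | 70.3 / 70.0 |
| Commune means | 0.10 | 0.05 | 0.026 / 0.048 | 64.2 / 75.1 |
| Commune means | 0.20 | 0.05 | 0.012 / 0.049 | 56.1 / 78.5 |

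Power forgone by omitting strata:

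- Individual-level test, ICC 0: 82.8 − 80.0 = 2.8 points at R² 0.10, and 85.9 − 80.9 = 5.0 points at R² 0.20.
- Commune means, ICC 0.05: 75.1 − 64.2 = 10.9 points, and 78.5 − 56.1 = 22.4 points.
- Commune means with four strata, ICC 0.05: 70.7 / 69.5 at R² 0, 63.8 / 73.6 at 0.10 and 56.2 / 77.1 at 0.20. Adjusting for uninformative strata costs about one point.

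**4. Why commune means lose more.** Averaging shrinks caregiver noise but leaves stratum variance untouched. With 3.75 caregivers per commune and ICC 0.05, the variance of a commune mean within a stratum is (1 − R²) × (0.05 + 0.95/3.75) = 0.303 × (1 − R²). The stratum share of commune-level variance is R²/[R² + 0.303(1 − R²)]. That is 0.10/0.373 = 27% at R² 0.10 and 0.20/0.443 = 45% at R² 0.20.

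**5. Direction of the error in the planned test.** With residual ICC ρ, the ratio of the true to the assumed variance of the arm difference is about (1 − R²)(1 + 2.75ρ), where 2.75 = 3.75 − 1. A ratio below 1 makes the test conservative; above 1, anti-conservative.

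- R² 0.10: 0.90 × (1 + 2.75 × 0.04) = 1.00, so the conservatism is gone at ρ of about 0.04.
- R² 0.20: 0.80 × (1 + 2.75 × 0.09) = 1.00, so it is gone at ρ of about 0.09.

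The individual-level rows at R² 0.10 show the same: without strata, the type I error moves from 0.039 to 0.054 to 0.062 as the ICC goes from 0 to 0.05 to 0.10. Adding strata alone then raises it to 0.064 at ICC 0.05 and 0.073 at ICC 0.10.

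**The case against.** The strongest reply is that no harm can be shown. The strata are unnamed, so they may predict nothing. The planned outcome is a change score, so stable differences in burden between strata cancel and the strata would have to predict change itself. For the planned test the forgone gain is small even when they do. Balance is by commune, not by caregiver: with 3 to 15 caregivers per commune, numbers by stratum can still differ between arms. And this is a pilot of feasibility, acceptability and preliminary efficacy. All of that stands, and it limits the point to a conditional one.

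A reader might go further and infer that the planned test is conservative and that power falls below the SAP's 80%. Suppose a two-sided 5% test, no residual clustering, and strata explaining a share f of the variance of the arm difference. The type I error is then 2 × [1 − Φ(1.96/√(1 − f))], which gives 3.9%, 2.8% and 1.9% at f = 0.10, 0.20 and 0.30. Power, 1 − Φ(1.96/√(1 − f) − 2.80), is 77%, 73% and 68%. The arithmetic is right, but the documents do not support the inference:

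- Those power figures are measured against a hypothetical stratified analysis set at 80%. The SAP's 80% was computed without strata, so leaving them out does not reduce it.
- The formula sets residual commune correlation to zero. At f = 0.10 and ρ = 0.05 the variance ratio is 0.90 × 1.1375 = 1.024, and the two-sided type I error is about 5.3%, not 3.9%.
- The SAP's power statement is one-sided.

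What the reply does not remove is the mismatch itself. The design fixes a factor that no analysis uses, and including it costs almost nothing even if it proves uninformative.

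**Conclusion.** The point holds in a limited form. Communes are randomised within strata, no planned analysis includes the strata, and the baseline-difference rule tends to keep them out.

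The consequence is forgone precision, not a shortfall from the stated power. Under the assumed R² of 0.10 to 0.20 it is about 3 to 5 points for the individual-level test. It is about 11 to 22 points for a commune-mean analysis at an assumed ICC of 0.05. It is nil if the strata do not predict the outcome.

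Whether the planned test is too conservative or too liberal cannot be settled from the documents. That depends on the unstated ICC as well as on the strata, and the two act in opposite directions. The strata therefore matter most once the analysis respects commune. These sizes come from a simulation with communes of 3 or 4 caregivers; the wider range that the protocol allows was not simulated.

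**What to change.** In the protocol, name the stratification factor(s) and state the number of strata.

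In the SAP, pre-specify stratum indicators in the primary analysis of ZBI-6 and of PHQ-4, whether or not the arms differ at baseline, and make that analysis account for commune. Any one of these would serve:

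- a mixed model with a commune random effect, stratum fixed effects and small-sample degrees of freedom;
- an analysis of commune-level summaries adjusted for stratum;
- a permutation test that re-assigns communes within strata.

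Do not add strata alone to the individual-level t-test or analysis of covariance: under the assumptions above that raises the type I error.

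The cost is a sentence or two, plus about one commune-level degree of freedom per extra stratum out of about 14 (16 communes less 2 arms). The strata should therefore be few.
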